14.0 Annual reporting

14.1 Development Safety Update Report (DSUR)

The DSUR will be written by the CI (following Sponsor procedures) and submitted to the sponsor for review prior to submission to the MHRA. The DSUR is due for submission within 60 days of the end of the reporting period. The reporting period is annually from the date on the "Notice of acceptance letter" from the MHRA. The sponsor's delegated Medical Assessor, usually the CI, will carry out a risk benefit analysis of the IMPs encompassing all events having arisen on the study. REC will be sent a copy of the DSUR.

15.0 Statistical and data analysis

15.1 Sample size calculation

A total of 36 participants will be recruited (randomised 1:3 control:intervention). The number of participants treated on each dose of Omegaven will be determined by the escalation / deescalation rule specified in the BOIN design shown in Figure 2 and Table 1, which aims to exclude a toxicity rate of ≥ 30%. The minimum number of participants to be treated on a single dose is nine and the maximum is 27. Assuming mortality of approximately 20-30% in critically ill patients, we will replace up to a maximum of three patients in each study phase in case of patient death, or withdrawal. There is no formal assessment of sample size required for a phase I dose escalation trial, however 36 participants (nine control and 27 intervention) will be sufficient to provide pilot data on the exploratory outcomes. A published study with eight patient samples per group enabled examination of the p38 inhibitor and identification of a doubling in proliferation and cytotoxicity as measured by granzyme and perforin expression using nine patients per group would provide almost 80% power to detect a mean difference of 12 in %CD107a CD8+ EMRA T cells (assuming SD=6 and α=0.05) (unpublished data, [name])¹⁵. Early phase trials often use less conservative type I error rates as they can be considered screening studies to inform a future definitive trial; with this sample size the trial would have 87.4% power for α =0.1 and 94.4% for α =0.2 using the parameters given above.

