The BOIN intervention algorithm for the HIPPO trial is shown in **Figure 2**. ³⁵ ³⁶ Cut-offs for the escalation and de-escalation boundaries for the DLT rate were obtained using software available at www.trialdesign.org, using the following input parameters:

- three doses
- target toxicity rate for the maximum tolerable dose 0.30 (30%)
- patients recruited in cohorts of nine,
- maximum sample size is 27
- 0.80 probability cut-off for overdose control

Upon the completion of each dosing phase (defined as at least five hours after the last patient in the phase has finished the last dose of Omegaven), the DLT rate will be computed as follows, and compared with the cut-offs shown in **Figure 2** before treating the next cohort of patients:

DLT rate = Number of patients who experienced DLT at current dose

Total number of evaluable patients treated on current dose

Following the DLT assessment and based on the DLT rate, the next nine intervention patients will either:

- 1) receive the next highest dose if the observed DLT rate on the current dose is ≤0.236
- 2) remain on the same dose if the observed DLT rate is >0.236 and <0.359
- 3) de-escalate to the next lowest dose if the observed DLT rate is >0.359

If de-escalation is indicated on the lowest dose, the next cohort of patients will continue at the lowest dose. If the probability of the observed DLT rate being greater than the target DLT is >0.80 and if at least three patients are treated at the current dose, the dose is too toxic. Therefore, this dose and any higher doses will be eliminated. If the lowest dose is too toxic, the trial must be terminated.

After the panel meeting that will be held following completion of each dosing phase, a report will be drafted and agreed on by all panel members in a timely manner. The report which will include the recommended dosing plan for the next cohort of patients will be signed off by the trial statistician within two weeks of receipt. Once these approvals are in place, the next cohort of patients will be recruited. These approvals will be filed in the ISF and TMF. Each DLT assessment report will also be reported to the Data Monitoring and Ethics Committee (DMEC) for information only.

[figure not shown]

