15.4 Statistical Analysis

After the completion of the dose-escalation (stopping rule met), the maximum tolerable dose (primary outcome) will be calculated using an isotonic regression considering the DLT events across all doses³⁵. This computation is implemented by the "BOIN" app available at http://www.trialdesign.org. The maximum tolerable dose is selected as the dose for which the isotonic estimate of the toxicity rate is \leq 0.359 and closest to the target toxicity rate (0.30). If there are ties, the higher dose level is selected when the isotonic estimate is lower than the target toxicity rate and the lower dose level is selected when the isotonic estimate is greater than or equal to the target toxicity rate.

Analyses of the exploratory outcomes will estimate dose-response effects of Omegaven, using the data from the control group as a comparator. Analyses of the exploratory clinical and laboratory outcomes will primarily use descriptive statistics. Quantitative data will be summarised by group, using descriptive statistics including mean (standard deviation) or median (interquartile range), as appropriate. Categorical data will be summarised by group, using frequencies and percentages. Further exploratory analysis of the laboratory outcomes will use repeated measures analysis of covariance including data at all follow-up time-points to compare each dose level with concurrently randomised controls, adjusting for baseline values. Differences between groups will be described using point estimates and 95% confidence intervals.

Given that the majority of data collection will occur in hospital, we anticipate a low missing data rate. A full statistical analysis plan will be drawn up prior to analysis, and will include handling of missing data, outliers, protocol violations.

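### Section 15.1 says the BOIN rule aims to exclude a DLT rate of 30% or more, but the design targets 30% and does not exclude it

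*Protocol*

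**What the plan says.** Protocol section 15.1 (Sample size calculation) says that the number treated on each dose follows the BOIN escalation and de-escalation rule, "which aims to exclude a toxicity rate of ≥ 30" per cent. For that rule it points to Figure 2 and Table 1.

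The sections that define the rule say something different:

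- Section 2.6 (dose-escalation plan) lists among the design inputs "target toxicity rate for the maximum tolerable dose 0.30 (30" per cent), with "patients recruited in cohorts of nine", "maximum sample size is 27" and "0.80 probability cut-off for overdose control".
- The same section escalates at an observed DLT rate of 0.236 or less, stays on the dose between 0.236 and 0.359, and de-escalates above 0.359. Its worked example after Table 3 treats nine more patients at the same dose when 3 of 9 have a DLT.
- Section 15.4 (Statistical Analysis) names as MTD the dose whose isotonic estimate is at most 0.359 and "closest to the target toxicity rate (0.30"). Its tie rule provides for estimates at or above the target.

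**The concern.** A rule that looks for the dose nearest 30%, keeps treating at an observed 33.3%, and may select a dose estimated at or above 30% is not a rule for excluding 30% or more. Section 15.1 therefore states an aim that sections 2.6 and 15.4 do not pursue.

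The MTD is the trial's only primary outcome, and section 6.2 places the trial ahead of a larger efficacy trial. Section 15.1 is the protocol's account of what the dose-finding sample is for, and it gives no operating characteristics. If the stated aim is carried into the report, the selected dose could be described as one for which a DLT rate of 30% or more has been ruled out. The design cannot support that statement.

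**Working it through.** **Inputs from the protocol.** Section 2.6: three doses, target φ = 0.30, cohorts of nine, at most 27 treated patients, elimination cut-off 0.80, boundaries 0.236 and 0.359, and the decision counts in Table 3. Section 15.4: isotonic estimate, cap 0.359, closest to 0.30.

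**Inputs assumed.** The usual BOIN defaults p1 = 0.6φ = 0.18 and p2 = 1.4φ = 0.42; a uniform Beta(1,1) prior for the elimination rule; all cohorts fully evaluable; the true DLT rates below, because the protocol gives none.

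**1. Reproduce the plan's boundaries.**

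- λe = ln[(1−p1)/(1−φ)] / ln[φ(1−p1)/(p1(1−φ))] = ln(0.82/0.70) / ln(0.246/0.126) = 0.2365
- λd = ln[(1−φ)/(1−p2)] / ln[p2(1−φ)/(φ(1−p2))] = ln(0.70/0.58) / ln(0.294/0.174) = 0.3585

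These agree with 0.236 and 0.359. With the uniform prior and the 0.80 cut-off, the escalate, de-escalate and eliminate rows of Table 3 also reproduce in all 25 columns. The rule is correctly specified for a 30% target.

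**2. What the elimination rule keeps.** With y patients with a DLT among n treated, the posterior is Beta(1+y, 1+n−y). The dose is eliminated if P(rate > 0.30) > 0.80.

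| Patients with DLT | Observed rate | P(rate > 0.30) | Result |
|---|---|---|---|
| 3/9 | 33.3% | 0.650 | kept |
| 4/9 | 44.4% | 0.850 | eliminated |
| 6/18 | 33.3% | 0.666 | kept |
| 7/18 | 38.9% | 0.818 | eliminated |
| 9/27 | 33.3% | 0.682 | kept |
| 10/27 | 37.0% | 0.809 | eliminated |

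A dose can thus be retained when it is about twice as likely as not to exceed 30%. With full cohorts the highest rate that can be selected is 33.3%. The written cap of 0.359 is approached only with incomplete cohorts, for example 5/14 = 0.357.

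**3. One cohort.** With a true rate of 30%, nine patients give 2 or fewer with a DLT (escalate) with binomial probability 46.3%, and 3 or fewer (not eliminated) with probability 73.0%. At a true rate of 35% these are 33.7% and 60.9%.

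**4. Whole trial.** Exact enumeration of three cohorts of nine under Table 3, then isotonic estimation and the section 15.4 selection rule:

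| Assumed true rates | Lowest dose named | Middle dose named | Top dose named | Any MTD named | No MTD |
|---|---|---|---|---|---|
| 30/40/50% | 42.7% | 16.1% | 2.7% | 61.5% | 38.5% |
| 35/45/55% | 34.8% | 8.0% | 0.8% | 43.6% | 56.4% |
| 40/50/60% | 23.8% | 3.3% | 0.2% | 27.3% | 72.7% |
| 50/60/70% | 6.7% | 0.3% | 0.0% | 7.0% | 93.0% |

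Every dose in these rows has a true rate of 30% or more, so a design that excluded such rates would rarely name any of them. In the first row, 42.7 points are the 30% dose and 16.1 + 2.7 = 18.8 points (18.9 before rounding) are the 40% or 50% dose.

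**The case against.** The strongest reply is that the clause is a passing description. Target, boundaries, elimination cut-off, Table 3 and MTD selection are set out explicitly and consistently elsewhere, and section 15.1 says no formal sample size assessment is required. No number is derived from the clause, and nobody running or analysing the trial would act differently because of it. The 0.80 rule also gives real overdose control, as the 50/60/70% row shows. All of this stands. It limits the point to the stated aim but does not make that aim true.

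Several stronger readings are tempting, and the documents do not support them:

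- *The protocol claims the chosen dose will be shown to be below 30%.* It speaks only of an aim, and the 30% target is plain in sections 2.6 and 15.4. The risk lies in what a reader may infer.
- *The design wrongly selects a toxic dose in 61% of trials.* Most of that figure is the 30% dose, the intended answer. All the scenarios are assumptions; under 10/15/20% no dose is at 30%.
- *Doses estimated at up to 35.9% will be accepted.* That is the nominal cap. With full cohorts the limit is 33.3%.
- *The next sentence of 15.1 is wrong because a dose may go untested.* "The minimum number of participants to be treated on a single dose is nine and the maximum is 27" reads naturally as referring to a dose that is used, and section 2.6 already says the trial may stop whichever doses have been tested.
- *Only results such as 0/9 or at most 3/27 put an upper confidence limit below 30%.* This overlooks 18 patients on a dose: 1/18 gives a one-sided 95% upper limit of 23.8%.

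**Conclusion.** The concern holds as a misstated aim in section 15.1. The protocol's own rules target a DLT rate of 30%, retain 33.3%, and may select an estimate at or above 0.30, so exclusion of 30% or more is not a property of the design. That part needs no assumption about true rates.

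The size does depend on assumptions. With full cohorts and every dose truly at 30% or more, an MTD is named in about 61%, 44% and 27% of trials when the lowest dose is at 30%, 35% and 40% in the scenarios above, and in 7% when it is at 50%.

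The escalation rules are not in error and the conduct of the trial is unaffected. What changes is what the trial may conclude about its primary outcome.

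**What to change.** In section 15.1, replace the clause with: *aims to identify the dose whose DLT rate is closest to the 30% target, eliminating doses for which P(DLT rate > 0.30) > 0.80; it does not establish that the selected dose has a DLT rate below 30%*. In the same sentence, change the cross-reference from Table 1, which defines the DLTs, to Table 3, which holds the escalation rule.

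If the sponsor does intend to exclude rates of 30% or more, rewording is not enough: the stated aim and the design parameters must be reconciled.

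Optional: add *for any dose used* to the sentence on the minimum of nine, and report the DLT rate at the MTD with an exact interval and the posterior probability that it exceeds 0.30. The latter can be left to the SAP.

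The cost is one sentence of text and a less favourable claim. Sample size, escalation rules and conduct stay as they are.

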Figure 2 Intervention algorithm: The figure describes the BOIN dose-escalation and de-escalation plan for the HIPPO trial. At each stage, the DLT events rate will be used to assess whether the dose will be escalated, retained, or de-escalated. The stopping rule at each dosing phase is defined as "Is the maximum sample size reached?". After the stopping rule is met, the maximum tolerable dose (MTD) will be calculated, which is the primary outcome of the trial. Note: If the lowest dose is eliminated due to

DLT = Dose-limiting toxicity, from a list of pre-specified adverse or serious adverse events attributable to Omegaven (Table 1).

toxicity the trial is stopped, and no maximum tolerable dose can be obtained.

BOIN design implementation

The following steps detail the BOIN design implementation plan for the HIPPO trial.

- 1. Treat patients in the first cohort (nine patients) at the lowest dose (0.2 g/kg/d) of Omegaven
- 2. Perform DLT assessment as described above
- 3. Calculate DLT rate

DLT rate = Number of patients who experienced DLT at current dose

Total number of evaluable patients treated on current dose

- 4. Assign a dose to the next cohort of patients:
 - Conduct dose-escalation/de-escalation according to the rule displayed in **Table 3**. Notes for using Table 3:
 - a. "Eliminate" means eliminate the current and higher doses from the trial to prevent treating any future patients at these doses because they are overly toxic.
 - b. When a dose is eliminated, the next cohort is automatically de-escalated to the dose on the next lower level. When the lowest dose is eliminated, the trial is stopped for safety. In this case, no dose should be selected as the maximum tolerable dose.
 - c. If none of the actions (i.e., escalation, de-escalation or elimination) is triggered, the new cohort of patients are treated at the current dose.
 - d. If the current dose is the lowest dose and the rule indicates dose de-escalation, the new cohort of patients should be treated at the lowest dose unless the number of DLT events reaches the elimination boundary, at which point the trial is stopped for safety.
 - e. Number of DLT events in **Table 3** is the number of patients with at least one DLT events, therefore a patient will only be counted once for DLT events assessment, independent of the number of DLT events the patient experiences.

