- Repeat step four until the maximum sample size of 27 patients receiving the intervention is reached, or stop the trial early if the number of patients experiencing DLT events at the lowest dose level reaches the elimination boundaries listed in **Table** In the latter case, no dose should be selected as the maximum tolerable dose.

Table 3 Escalation/De-escalation Rule for the HIPPO trial: The table details the rules when to escalate, retain, de-escalate or eliminate a treatment dose in the HIPPO trial, based on number of patients with DLT events (Table 1), considering the total number of patients treated with that dose. For HIPPO, cohorts of nine (highlighted columns) are treated. The last row represents the number of patients with DLT events at which the dose is deemed too toxic, and that dose and any higher dose will be eliminated.

Escalation/De-escalation Rule

Number of evaluable patients treated	3	4	5	6	7	8	9	10	11	12	13	14	15	16	17	18	19	20	21	22	23	24	25	26	27
Escalate if # of DLT <=	0	0	1	1	1	1	2	2	2	2	3	3	3	3	4	4	4	4	4	5	5	5	5	6	6
Stay if # of DLT =	1	1	NA	2	2	2	3	3	3	3-4	4	4-5	4-5	4-5	5-6	5-6	5-6	5-7	5-7	6-7	6-8	6-8	6-8	7-9	7-9
De-escalate if # of DLT >=	2	2	2	3	3	3	4	4	4	5	5	6	6	6	7	7	7	8	8	8	9	9	9	10	10
Eliminate if # of DLT >=	2	2	3	3	3	4	4	5	5	5	6	6	6	7	7	7	8	8	8	9	9	9	10	10	10

DLT = dose-limiting toxicity

of DLT is the number of patients with at least 1 DLT

NA = not applicable (no rule available for staying on same dose in this scenario – plan is to either escalate or deescalate)

Further notes:

Dose-escalation will occur if applicable, to the second (0.4 g/kg/d Omegaven) and third dose (0.6 g/kg/d Omegaven). If no dose-escalation can be performed, another nine participants will either be treated at the same or the lower dose, guided by the dose-escalation plan, leading to 27 patients receiving the intervention, and an additional 9 patients in the control group, to reach the maximum sample size of 36 patients.

The trial will stop if the stopping rule is met (once the maximum sample size for the trial has been reached), irrespective of which doses have been tested; or if the elimination rule is met on the lowest dose (the lowest dose is found to be too toxic) (lowest row in **Table 3**). The maximum sample size for this trial is 36 patients (27 patients receiving the intervention in cohorts of 9 patients, plus 9 control patients).

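### When the 27-patient cap is reached, section 15.4 can name a maximum tolerable dose although Table 3 still says escalate to a dose never given

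*Protocol*

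**What the plan says.** Section 2.6 sets the design inputs: three doses, a target DLT rate of 0.30 and a 0.80 cut-off for overdose control. It describes recruitment as "patients recruited in cohorts of nine", up to 27 intervention patients in all. The first implementation step is "Treat patients in the first cohort (nine patients) at the lowest dose (0.2 g/kg/d) of Omegaven". After each cohort the dose moves by at most one level.

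For nine evaluable patients, Table 3 gives escalate at 2 or fewer patients with a DLT, stay at 3, and de-escalate and eliminate at 4 or more. The further notes to Table 3 fix the stopping point: "The trial will stop if the stopping rule is met (once the maximum sample size for the trial has been reached), irrespective of which doses". (The clause ends by referring to the doses given up to then.) The one case in which section 2.6 withholds an MTD is elimination of the lowest dose.

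Section 2.3 defines the primary outcome as the MTD across the three planned doses. Section 15.4 selects it as the dose whose isotonic estimate is no more than 0.359 and closest to 0.30. Ties below the target go to the higher dose.

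On numbers per dose, section 15.1 says: "The minimum number of participants to be treated on a single dose is nine and the maximum is 27".

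**The concern.** With three cohorts and three doses, there is no spare cohort. The top dose is reached only if both of the first two cohorts escalate, so a single stay uses the cohort that 0.6 g/kg/d would have needed. The final cohort can then bring the cumulative rate at the current dose down to the escalation boundary when no patients are left to act on it.

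At that point the plan's two rules give different messages. Table 3 says the data call for the next dose to be tested. Section 15.4 calls the current dose the maximum tolerable one. No toxicity finding has marked it as a maximum; it is only the last dose reached before the patients ran out. Section 6.2 presents the trial as preparation for a larger efficacy trial, which could then inherit this dose as a toxicity ceiling.

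**Working it through.** **1. Reproduce the plan's boundaries.** Inputs are the target of 0.30 and the cut-off of 0.80 (section 2.6). I assume the usual BOIN limits of 0.6 and 1.4 times the target (0.18 and 0.42), which the protocol does not state.

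- Escalation: ln(0.82/0.70) / ln[(0.30 × 0.82)/(0.18 × 0.70)] = 0.1582/0.6690 = 0.2365.
- De-escalation: ln(0.70/0.58) / ln[(0.42 × 0.70)/(0.30 × 0.58)] = 0.1880/0.5245 = 0.3585.
- At n = 9, 18, 27 this gives escalate at ≤2, 4, 6 and de-escalate at ≥4, 7, 10. Elimination (uniform prior, probability above 0.80) is at ≥4, 7, 10.

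All of these match the printed boundaries and Table 3.

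**2. Reachable numbers.** With nine evaluable patients per cohort, the possible totals at 0.2/0.4/0.6 g/kg/d are (9,9,9), (9,18,0), (18,9,0) and (27,0,0). If the lowest dose is eliminated early, they are (9,0,0) or (18,0,0).

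**3. Paths that end on escalate with the next dose neither tested nor eliminated.** Counts are cumulative patients with a DLT at that dose.

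- Path A: 3/9 at 0.2, then 3–4/18 at 0.2, then ≤2/9 at 0.4.
- Path B: ≤2/9 at 0.2, then 3/9 at 0.4, then 3–4/18 at 0.4.
- Path C: 3/9, then 5–6/18, then 5–6/27, all at 0.2.

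**4. What section 15.4 names.** On paths A and B the isotonic estimate at 0.4 lies between 3/27 = 0.111 and 4/18 = 0.222. For example, 3/18 at 0.2 followed by 0/9 at 0.4 pools to 3/27. The estimate at 0.4 is never below that at 0.2, and ties below 0.30 go to the higher dose, so 0.4 is named. On path C the estimate is 5/27 = 0.185 or 6/27 = 0.222, and 0.2 is named. Every estimate is below 0.236.

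**5. Probabilities.** Let p1 and p2 be the true DLT rates at 0.2 and 0.4, b(k;p) the binomial probability of k out of 9, and B(k;p) its cumulative form.

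- A = b(3;p1) × B(1;p1) × B(2;p2)
- B = B(2;p1) × b(3;p2) × B(1;p2)
- C = b(3;p1) × [b(2;p1) × B(1;p1) + b(3;p1) × b(0;p1)]

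For rates of 10/20/30%:

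- A = 0.0446 × 0.7748 × 0.7382 = 0.0255
- B = 0.9470 × 0.1762 × 0.4362 = 0.0728
- C = 0.0446 × [0.1722 × 0.7748 + 0.0446 × 0.3874] = 0.0067
- Total = 0.105

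| Assumed rates at 0.2/0.4/0.6 | A | B | C | Total |
|---|---|---|---|---|
| 5/10/20% | 0.7% | 3.4% | 0.05% | 4.2% |
| 10/20/30% | 2.6% | 7.3% | 0.7% | 10.5% |
| 15/20/25% | 4.7% | 6.6% | 1.9% | 13.3% |
| 20/30/40% | 3.6% | 3.9% | 2.7% | 10.2% |

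The rate at 0.6 does not enter the total, because 0.6 is never given on these paths.

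**6. The related case at the top dose.** The probability that 0.6 is tested is B(2;p1) × B(2;p2). That is 0.9470 × 0.7382 = 70% for 10/20/30%, and 94%, 63% and 34% in the other three rows, top to bottom. The probability that 0.6 is tested and has ≤2/9 is 0.699 × 0.463 = 32% for 10/20/30%, and 69%, 38% and 8% in the other rows. Section 15.4 does not say how that outcome should be described either.

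**The case against.** The best defence is that nothing is hidden. The cap is fixed and disclosed, section 2.6 says the trial stops there whichever doses were reached, and section 15.4 gives a complete selection rule. Ending on escalate then follows from a small fixed maximum and is not a contradiction. Section 15.4 also promises a full statistical analysis plan, and the affected share is at most about 13% in the scenarios examined. The cap is indeed a legitimate choice, and I do not question it. But the protocol itself fixes how the sole primary outcome is selected, and that rule, followed as written, yields a conclusion that Table 3 does not support.

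A second fair objection is that relabelling only these paths would be uneven. When 0.6 is tested with few DLTs, it too is merely the highest dose tested. That stands, and the fix covers it.

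A reader might also infer two stronger charges from section 15.1, and the documents support neither.

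- *The range of 9 to 27 is an arithmetic error.* It is not. Any opened dose receives 9, 18 or 27 patients. Only a qualifier is missing: 27 is possible only at 0.2, and the two upper doses may receive none. The same section says the escalation rule determines the number on each dose.
- *The stated power is not delivered at the upper doses.* Section 15.1 says "with this sample size the trial would have 87.4% power for α =0.1 and 94.4% for α =0.2 using the parameters given above", and section 15.4 plans "to compare each dose level with concurrently randomised controls, adjusting for baseline values". A two-sided t-test with difference 12, SD 6 and nine patients on a dose against three concurrent controls has power 77.1%, 87.4% and 94.4% at α = 0.05, 0.1 and 0.2. Every opened dose meets the printed figures. They are lacking only if a dose is never opened, and section 15.1 calls these pilot data for exploratory outcomes.

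**Conclusion.** The point holds as a gap in the primary-outcome rule. At the cap, section 15.4 can attach the MTD label to a dose with an estimated DLT rate below the escalation boundary when a higher planned dose was neither given nor ruled out. The probability is about 4% to 13% over the four scenarios. Those scenarios are assumptions, since the protocol states no expected DLT rates. The figures also assume nine evaluable patients in each cohort; with fewer, other columns of Table 3 apply and the probabilities shift.

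This is a cheap improvement to how the result is reported. It shows no fault in the sample size, the boundaries or the stated power.

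**What to change.** Add two reporting rules to section 15.4.

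1. If the maximum sample size is reached while Table 3 indicates escalation at the highest tested dose, and the next planned dose was neither tested nor eliminated, report the result as *highest dose tested; MTD not reached*, with the isotonic estimate.
2. If 0.6 g/kg/d is tested and at most 2 of 9 patients have a DLT, state that the MTD is at or above the highest planned dose.

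Both concern wording of the result only. They need no extra patients and alter no dose, cohort or escalation rule. The cost is a weaker primary conclusion in the trials concerned.

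Optionally, clarify in section 15.1 that 9 to 27 applies to any dose that is opened (before replacements, 0 to 18 at 0.4 and 0 or 9 at 0.6), and that the power figures are conditional on the dose being opened.
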